**Secondary outcome variable(s)**

The consistent accuracy of the diagnostic device

**Background**

Outpatient diagnostics are slow and expensive. This comes from long turnaround times, difficult workflows, and high costs. Turnaround time for diagnostics tests can be up to 10 days or more, as patients have to travel to a separate facility to have labs drawn, and those lab draws follow a complex workflow. Since testing is offsite, a significant number of patients never make it to their appointments and are therefore not retained in the system. Time delay or non-compliance can make acute problems even more serious. Additionally, lab samples have to be sent to a third location to have actual clinical testing performed on them. This causes patients to be lost to follow up when doctors attempt to provide patients with results, but are unable to get in touch. Beyond time and workflow difficulties, tests can cost anywhere from \$15-100 per test depending on a myriad of factors such as insurance, plan

coverage, and provider. Given that over two-thirds of all clinical decisions are based on laboratory testing (COLA, 2015) and in a 2002 survey of the US, 77% of providers were unable to contact their patients with abnormal diagnostic results (White, 2002), diagnostics are not working efficiently for outpatient providers. These studies show that lack of access to fast point of care results leads to significant problems in continuum of care and effective care. Very few point of care (POC) diagnostics are used by doctors, as modular machines are often cost or workflow prohibitive. Many POC diagnostics require a trained technician and have high cost hardware and certifications. The POC diagnostics that are often used are tests such as pregnancy tests or rapid strep tests that are multiple different platforms and are rate-limited in how many tests a practice can adopt. Group K is revolutionizing healthcare through innovative POC diagnostics. We solve the inefficiencies of current lab solutions by bringing the "lab" to the provider and allowing practitioners to run diagnostic tests onsite in doctors offices and clinics. With a low cost, reliable system providers have actionable information before the patient leaves the office. Doctor offices will be able to pay a low cost for the product and bill insurers for running diagnostics. Group Ks quick, inexpensive, and accurate diagnostic platform will be able to improve care for patients all around the world. Group K is developing a paper microfluidic platform with an accompanying mobile application(app). The paper microfluidic device is a simple, inexpensive wax backed device with three testing areas. These areas have a mix of dried proprietary reagents that when combined with a patients drop of blood, or in the future, saliva or urine, will produce results in a color change. An app is then used to interpret the color change and output results to a doctor.

### ***Study Design***

#### **Phase\***

Not applicable

#### **Design**

The design of the study is to investigate 200-400 patient finger prick samples to prove the ability of Group Ks Diagnostic app to identify liver function values on the multidiagnostic. The values will be stored on a Penn Server correlating the patient data obtained from the multidiagnostic with a random code, and then the random code correlated to the patient identifier (name and date of birth) and then the patients record of the results of their standard liver function test.

#### **Study duration**

The estimated length of the study will be approximately one year. Recruitment will be approximately 4 months. Subjects will participate in one study visit during a previously scheduled clinic visit or during an inpatient hospital admission.

#### **Resources necessary for human research protection**

Describe research staff and justify that the staff are adequate in number and qualifications to conduct the research. Describe how you will ensure that all staff assisting with the research are adequately informed about the protocol and their research related duties. Please allow adequate time for the researchers to conduct and complete the research. Please confirm that there are adequate facilities for the research.

All investigators and study staff on this protocol are well trained on the study and all have current CITI certifications. Subjects will only be seen by the PI and members of the research study in a private clinic room. Patients will be given ample time to have all of their questions answered.

## **Characteristics of the Study Population**

#### **Target population**

The target population is adults (18 years and old) with varying liver health who have had a hepatic function panel or equivalent tests completed at the same day as their finger prick sample obtained; ALT, AST, ALP, albumin, bilirubin and total protein.

#### **Subjects enrolled by Penn Researchers**

400

### Subjects enrolled by Collaborating Researchers

0

#### Accrual

The study population will be drawn from adults who have an indication to perform liver function tests during their GI clinic visit or during an inpatient hospital admission. The investigators on this protocol are the Hepatology physicians and therefore will be treating these patients as standard of care. [name] and the research staff will identify subjects.

#### Key inclusion criteria

1. Have a liver function testing for the required 6 tests completed (ALT, AST, ALP, albumin, bilirubin, and total protein) 2. 18 years or older

#### Key exclusion criteria

1. Inadequate blood sample obtained from finger stick 2. Inconclusive liver function testing 3. Not all 6 liver tests completed on the same sample 4. Liver tests not drawn for normal method at same time as finger stick.

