### **Procedures**

All patients, 18 years or older, with varying degrees of liver health seen in the Penn Gastroenterology clinic and/or who have been prescribed liver function testing to be drawn the same day as their clinic visit or inpatient hospital admission will be approached for consent. A finger prick will be collected after receiving consent. Blood sample will be tested with Group K's device. These results will be compared to results from a standard hepatic function panel or equivalent test (ALT, AST, ALP, albumin and total protein).

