### **Data Disclosure**

Will the data be disclosed to anyone who is not listed under Personnel?

De-identified data will be disclosed to Group K Diagnostics. Blood and corresponding results, will be

linked to original results via unique random identifiers. The linking set will be maintained and kept on an encrypted, password protected computer o HUPs servers. All information will be de-identified prior to Group K receiving it for FDA submission. Group K will receive confirmation that patient was above the age of 18 years old along with the results from Penn Pathology and the result from our device.

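### Exclusion criterion 1 makes a failed finger stick, known only after consent, an eligibility exclusion, so the secondary accuracy outcome covers only successful samples and gives no rate of failure to obtain a result

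*Protocol*

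**What the plan says.** Under Key exclusion criteria, the first item is "1. Inadequate blood sample obtained from finger stick". Under Procedures, "A finger prick will be collected after receiving consent". The secondary outcome is "The consistent accuracy of the diagnostic device"; the primary outcome is the regression curve and correlation coefficient.

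The Design section plans 200 to 400 finger-prick samples, and the enrolment entry for Penn researchers is 400. The Analysis Plan makes each data point one observation or test run. The Abstract says that the work supports FDA approval documentation.

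Two neighbouring rules are relevant. Inclusion criterion 1 is "Have a liver function testing for the required 6 tests completed" and exclusion criterion 3 is "Not all 6 liver tests completed on the same sample". Criteria 2 and 3 do not say which method they concern, whereas criterion 4 does: "Liver tests not drawn for normal method at same time as finger stick".

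**The concern.** An eligibility criterion should be decidable before the study procedure. This one can be decided only once the procedure has been tried, and the procedure is the sampling step of the method being validated. A participant whose stick fails has consented and been pricked, and is then defined out of the study population.

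At stake is how often the finger-stick method produces a result at all. Accuracy among successful samples is a legitimate quantity, but a statement about consistency for a regulatory file is incomplete without the failure rate. Because the exclusion is fixed in the protocol, a later analysis plan that tabulated failures would be working against a criterion that says those people do not belong in the study.

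**Working it through.** **Sequence.** Consent comes first, then the finger prick (Procedures), then exclusion if the sample is inadequate (Key exclusion criteria). Adequacy cannot be known at enrolment.

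**Is a failed stick counted elsewhere?**
- Primary outcome: it needs a device reading, so a failed stick contributes nothing whether or not criterion 1 exists.
- Secondary outcome: it names accuracy, which also needs a reading.
- Analysis Plan: one data point per observation or test run, so a stick with no run gives no data point.
- Data Disclosure: the developer receives an age confirmation "along with the results from Penn Pathology and the result from our device"; a failed stick has no device result.

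No section counts failed attempts, and none says that they go unrecorded.

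**Figures.** The protocol states no failure rate and no derivation of its sample size, so there is no planned figure to reproduce. The failure counts below are assumptions. They show what the planned numbers could tell us if every attempt were counted, using exact (Clopper-Pearson) 95% limits:

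| Assumed failure rate | 400 attempts | 200 attempts |
|---|---|---|
| 0% | 0/400: 0 to 0.9% | 0/200: 0 to 1.8% |
| 2% | 8/400: 0.9 to 3.9% | 4/200: 0.5 to 5.0% |
| 5% | 20/400: 3.1 to 7.6% | 10/200: 2.4 to 9.0% |
| 10% | 40/400: 7.2 to 13.4% | 20/200: 6.2 to 15.0% |

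The planned size would thus estimate the failure rate usefully.

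**Effect on usable samples if failures count toward the 400.** Usable samples are 400 × (1 − f), and interval width grows by 1/√(1 − f), taking width as proportional to 1/√n.
- f = 2%: 392 usable, intervals 1.0% wider
- f = 5%: 380 usable, 2.6% wider
- f = 10%: 360 usable, 5.4% wider

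All stay within the 200 to 400 of the Design section.

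**All-six rule.** If the regression is run analyte by analyte (six distinct quantities suggest it, but the protocol does not say so), inclusion criterion 1 and exclusion criterion 3 discard valid pairs for the other analytes when one is missing. The loss is zero if tests fail all together. Otherwise it depends on per-test failure rates and their dependence, which the protocol does not give, so I put no number on it.

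**The case against.** The strongest reply is that no stated outcome is biased. The secondary outcome names accuracy, not yield, and accuracy can be judged only where a reading exists. On this view the request is for an additional outcome. The list sits in a fixed-heading IRB form, and criteria 2 to 4 also concern test results or timing, so it reads as a definition of an evaluable sample. All participants sign consent, so consented minus evaluable could be counted, and enrolling 400 for 200 to 400 samples leaves room for unusable ones.

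Much of this stands. Leaving failed sticks out of the regression is unavoidable. The supporting sections are thin: Data Disclosure describes what leaves the institution, not the analysis population, and the Background sentence "With a low cost, reliable system providers have actionable information before the patient leaves the office" is about the developer's platform, not a study claim. What does not fall is the point itself. The criterion is written as an exclusion from the study, and consented minus evaluable would not separate failed sticks from other reasons.

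A reader might infer four stronger things that the document does not support:
- **That the primary result is distorted.** A sample without a reading adds no regression point.
- **That failures are concealed.** The protocol does not say that they go unrecorded.
- **That the 90% detection requirement is overstated.** In the Analysis Plan it sets the functional lower and upper limits; a failed stick is not a non-detection at a given level.
- **That criteria 2 and 3 hide device failures.** The Abstract, Design and Key inclusion criteria favour reading them as the standard panel. Only if they also cover the device would inconclusive or partial device runs be removed.

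**Conclusion.** The point holds for criterion 1. An outcome of the study procedure is written as an eligibility exclusion, so the secondary outcome describes successful samples only and carries no rate of failure to obtain a result. The regression and correlation are unaffected by it. The size is unknown because the protocol gives no failure rate; the percentages above illustrate precision and do not estimate the problem. The conclusion rests on applying the criterion as written and on no other section restoring failed attempts. The change should be made, but it is a repair of definition and reporting, not evidence that the primary analysis is wrong. The all-six rule is a minor point whose gain is unknown and possibly zero.

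**What to change.** 1. Move criterion 1, and any device-side part of criteria 2 and 3, from eligibility to a non-evaluable-sample category.
2. Count every consented participant with an attempted finger stick. Report the inadequate-sample and no-result rates with exact 95% intervals beside the regression, and present accuracy as conditional on an adequate sample.
3. State that what remains of criterion 2 refers to the standard panel.
4. If analysis is by analyte, amend both criterion 3 and inclusion criterion 1 so that each analyte uses all its valid same-time pairs.
5. Report the counts removed by the Analysis Plan's procedural exclusions. These should not simply be carried forward: one restricts the data to tests run under laboratory conditions, while the Abstract describes use in a doctor's office and the section on resources for human research protection has subjects seen in a clinic room. These statements must be reconciled.
6. Separately, reconcile Procedures, which lists five tests without bilirubin, with Target population and Key inclusion criteria, which list six.

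**Cost.** Protocol wording, a failure log and one extra table. Failed sticks count toward the 400, with the modest loss of precision shown above. To reach 200 adequate samples, 200/(1 − f) gives 205, 211 or 223 attempts at an assumed 2%, 5% or 10% failure, well inside 400. The stated performance may look less favourable. The Current Status entry records no subjects enrolled at this modification, so on the document's own record the change could precede any data.

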**Modification Summary**

Please describe any required modification to the protocol. If you are using this form to submit an exception or report a deviation, enter 'N/A' in the box below.

This modification is to expand recruitment to include patients admitted to inpatient services at The Hospital of the University of Pennsylvania.

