**Primary outcome variable(s)**

Regression curve and correlation coefficient

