### **Analysis Plan**

Lowest level frequency of detection must be detected 90% of the time. This will become the functional lower limit. The same with the highest level of frequency. We will exclude any data from tests that did not follow standard operating procedures or were not performed in a controlled, laboratory setting as well as any blood that has expired before liver function tests were completed. Each data point will represent one observation or one test run. We will use regression methods to determine the linear relationship between standard lab results and Group K diagnostic's device. We will also determine the correlation coefficient and measure of scatter around the regression line. This will be shown in equation form and in the form of graphs. The dependent variable will be our test results, the independent variable the standard of care.

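### Does the lack of a stated tolerance for drawing the standard panel at the same time as the finger prick leave the primary analysis pairs undefined?

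*Protocol*

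**What the plan says.** The Target population section describes adults whose hepatic panel was "completed at the same day as their finger prick sample obtained". Item 4 of the Key exclusion criteria is tighter and removes subjects with "Liver tests not drawn for normal method at same time as finger stick". Neither place gives a tolerance.

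Under Procedures, "A finger prick will be collected after receiving consent", so the prick is tied to consent and the standard panel only to the day of the visit or admission. The Design section describes the data link as a chain in which a device result carries a random code, with "the random code correlated to the patient identifier (name and date of birth) and then the patients record of the results" of standard testing. The Modification Summary says the current change is to "expand recruitment to include patients admitted to inpatient services".

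The primary outcome is "Regression curve and correlation coefficient", and the Analysis Plan adds: "We will also determine the correlation coefficient and measure of scatter around the regression line". Under Data Disclosure, the device developer receives confirmation of adult age "along with the results from Penn Pathology and the result from our device".

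**The concern.** A finger prick and a separate venous draw cannot be literally simultaneous, so a same-time rule needs some limit before it can be applied. The Protocol gives none, and two sections appear to set different pairing rules: same day in one, same time in the other. An inpatient may have more than one panel, and the linkage text does not say which one is paired with the prick.

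If pairs taken hours apart were kept, true change in the analyte between the two collections would be counted as scatter of the device. The regression scatter would rise and the correlation fall for reasons unrelated to the device. The results are meant to support an FDA submission, and the file described for the developer lists no collection times, so the two sources of scatter could not be separated from that file.

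**Working it through.** **Do the two timing rules conflict?** Set side by side:

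| Protocol section | Timing of the standard panel |
|---|---|
| Protocol Description, Abstract, Procedures | day of the clinic visit, or the inpatient admission (who is approached) |
| Target population | day of the finger prick |
| Key exclusion criteria, item 4 | time of the finger prick |

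Each row is narrower than the one above. A population narrowed by an exclusion criterion is ordinary nesting. A pair drawn hours apart on one day meets the Target population text and fails item 4, so it is excluded.

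**Which panel is used for an inpatient with several?** Item 4 points to the one drawn with the prick. Item 3 requires all six tests on one sample. Study duration gives each subject one study visit. Together these identify the panel in all but contrived cases.

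**Is timing lost?** The Design text explains how codes connect to identifiers; it is not a list of variables collected. Data Protection ticks date elements among the identifiers. Subject Confidentiality and Data Disclosure both say the linking set is kept, so the study team can go back to the source record. The Protocol names no clock time for the prick, but silence in privacy and linkage text does not show that none is recorded.

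**How large could an effect be?** The Protocol gives no figure to reproduce and no inputs. Assume device value = standard value + device error (SD s) + true change between collections (SD k·s, present in a share f of pairs), with independent terms and an error-free standard panel. Then

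- scatter multiplier = √(1 + f·k²)
- r = 1/√(1 + (1/r0² − 1)(1 + f·k²)), where r0 is the same-time correlation.

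If a quarter of pairs were late and kept (f = 0.25), with r0 = 0.95, so that 1/0.9025 − 1 = 0.108:

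| k | multiplier | r |
|---|---|---|
| 0.5 | √1.0625 = 1.03 | 0.947 |
| 1 | √1.25 = 1.12 | 0.939 |
| 2 | √2 = 1.41 | 0.907 |

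These values describe a case the Protocol excludes. With item 4 applied, pairs hours apart have f = 0 and the multiplier is √1 = 1.

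The real uncertainty is how far apart two samples may be and still count as taken together. Take the extreme in which every admitted pair carries some change (f = 1). A 10% rise in scatter needs 1 + k² = 1.21, so k = √0.21 = 0.46. True change over an interval short enough to pass as the same time would need an SD nearly half that of the device error, in every pair.

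**What does applying the exclusion cost?** Fisher's z with standard error 1/√(n − 3), at an assumed r of 0.95, gives a 95% interval of 0.939 to 0.959 with 400 pairs and 0.934 to 0.962 with 200. The Design section plans 200 to 400 samples and the enrolment figure is 400, so more than half the pairs would have to be lost to fall below the planned minimum.

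**The case for a change.** The strongest case for a change is that item 4 is an eligibility criterion in the Protocol and not an analysis detail, that it cannot be applied literally, and that nothing else in the document supplies the limit. Procedures ties the prick to consent, the Analysis Plan's data exclusions contain no draw interval, and date elements allow a same-day check at best. An analysis plan cannot restore a collection time that nobody wrote down. Adding inpatients makes several panels per subject possible. With no subjects enrolled, the repair is a line of text and two recorded times.

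Part of this stands. The tolerance is unstated, Procedures does not tie the prick to the venous draw, and the Protocol does not expressly require both times to be recorded. A one-line clarification would be cheap and reasonable.

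The step from there to an undefined set of analysis pairs does not stand. It requires item 4 to admit samples hours apart, which its wording rules out, and it infers from linkage and disclosure text that timing will not be held. The Analysis Plan also excludes tests that departed from standard operating procedures. Those are not shown, and they are a natural place for a collection interval.

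**Conclusion.** No change to the plan is needed. The same-day population and the same-time exclusion are nested, and followed as written they give a sound paired comparison using the panel drawn with the prick. The gap is an unwritten tolerance that study staff, operating procedures or an analysis plan would fill sensibly. Stating it would be a minor wording clarification.

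The Protocol does not allow the effect to be sized. The modelled loss in correlation, from 0.95 to between 0.947 and 0.907 with a quarter of pairs late, applies only if the exclusion is ignored. For the remaining ambiguity, a 10% rise in scatter needs k of at least 0.46 even with every pair affected. These values rest on assumed f, k and r0, with one value of each standing in for six different analytes. The conclusion assumes that item 4 is applied in its ordinary sense and that the study team can establish when the two samples were taken.

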#### Vulnerable Populations

Children Form

Pregnant women (if the study procedures may affect the condition of the pregnant woman or fetus) Form

Fetuses and/or Neonates Form

Prisoners Form

Other

None of the above populations are included in the research study

The following documents are currently attached to this item:

*There are no documents attached for this item.*

